7. MULTIPLE COMPARISONS AND MULTIPLICITY

No adjustments will be made for the preplanned multiple comparisons/endpoints.

8. SAFETY ANALYSIS

8.1. General

The safety analysis set (Section 3.3) will be used for all safety analyses. Summaries will be presented using descriptive statistics by treatment group as actually received unless otherwise stated. All data will be listed using ITT analysis set unless otherwise specified.

8.2. Duration of Exposure to Study Drug

Patients will be administered the study drug at visit 3 and receive a total of 4 sc injections in the abdomen.

The number of patients who received the study drug, the number of injection received, and reasons for IMP not administrated (adverse event or other) will be summarized using descriptive statistics.

IMP administration and IMP accountability data will be listed using safety analysis set.

8.3. Adverse Events

Adverse events will be recorded from time informed consent is obtained through the end of study participation.

All adverse events will be coded using MedDRA. Each patient will be counted only once in each preferred term or SOC category for the analyses of safety. Summaries will include treatment-emergent adverse events which are defined as adverse events occurring at or after the first dose of the IMP through the end of the follow-up visit. Listings will include all adverse events recorded.

Summaries will be presented for all adverse events (overall and by severity), adverse events determined by the investigator to be related to test IMP (defined as related or with missing relationship) (overall and by severity), serious adverse events, adverse events causing drug withdrawal or discontinuation from the study, protocol-defined adverse events of special interest (PDAESI), and PDAESI require completion of suspected anaphylaxis. Adverse events with the missing flag indicating serious will be excluded from the summary of serious adverse events but included in the summary of non-serious adverse events.

Listings for deaths, serious adverse events, adverse events leading to drug withdrawn or the study discontinuation, PDAESI, and PDAESI require completion of suspected anaphylaxis. In addition, listings for MedDRA dictionary terms for adverse event descriptions and adverse event preferred terms by patient number and treatment group will be presented.

Adverse events for patients who did not meet screening criteria will be listed.

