7.1.2. Recording and Reporting of Adverse Events

For recording of adverse events, the study period is defined for each patient as the time period from signature of the ICF to the end of the study. The period for reporting treatment-emergent adverse events is defined as the period after the first dose of IMP is administered until the end of the study.

All adverse events that occur during the defined study period must be recorded both on the source documentation and the CRF, regardless of the severity of the event or judged relationship to the IMP. For serious adverse events, the serious and protocol defined adverse event of special interest form (SAE/PDAESI form) must be completed and the serious adverse event should be reported within 24 hours of when the investigator becomes aware of the serious adverse event (Section 7.1.5.3.1). The investigator does not need to actively monitor patients for adverse events after the study period defined above (defined period).

At each contact with the patient, the investigator or designee must question the patient about adverse events by asking open-ended questions such as “Have you had any unusual symptoms or medical problems since the last visit? If yes, please describe.” A precise diagnosis should be recorded whenever possible. When such a diagnosis is made, all related signs, symptoms, and any test findings will be recorded collectively as a single diagnosis on the CRF and, if it is a serious adverse event, on the serious adverse event form. Reported or observed signs and symptoms that are not manifestations of a known diagnosis should be reported individually.

The clinical course of each adverse event will be monitored at suitable intervals until resolved, stabilized, or returned to baseline; or until the patient is referred for continued care to a health care professional; or until a determination of a cause unrelated to the IMP or study procedure is made.

The onset and end dates, duration (in case of adverse event duration of less than 24 hours), action taken regarding IMP, treatment administered, and outcome for each adverse event must be recorded both on the source documentation and the CRF.

The relationship of each adverse event to IMP and the severity and seriousness of each adverse event, as judged by the investigator, must be recorded as described below.

Further details are given in the Safety Monitoring Plan.

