9.7. Safety and Tolerability Analysis

The secondary safety and tolerability endpoints are:

- frequency of adverse events
- changes from baseline in clinical laboratory test results (serum chemistry, hematology, and urinalysis) throughout the study
- changes from baseline in vital signs (blood pressure, pulse rate, respiratory rate, and body temperature) throughout the study
- changes from baseline in 12-lead electrocardiogram (ECG) findings throughout the study
- use of concomitant medication
- local tolerability
- number (%) of patients who did not complete the study due to adverse events

Safety analyses will be performed on the safety analysis set (Section 9.2.3).

Safety assessments and time points are provided in [Table 2](#).

All adverse events will be coded using the Medical Dictionary for Regulatory Activities (MedDRA). Each patient will be counted only once in each preferred term or system organ class (SOC) category for the analyses of safety. Summaries will be presented for all treatment-emergent adverse events (overall and by severity), adverse events determined by the investigator to be related to test IMP (ie, reasonable possibility) (defined as related or with missing relationship) (overall and by severity), serious adverse events, and adverse events causing withdrawal from the study. Summaries will be presented by treatment group and for all patients. Patient listings of all adverse events, serious adverse events and adverse events leading to withdrawal will be presented.

Values and changes from baseline in clinical laboratory, ECG, and vital signs measurement data (including the incidence of abnormalities) will be summarized descriptively.

Local tolerability at the injection site (erythema, ecchymosis, induration, tenderness, warmth, swelling, and pain) will be assessed using standardized scales and summarized descriptively.

The use of concomitant medications will be summarized by therapeutic class using descriptive statistics.

For continuous variables, descriptive statistics (n, mean, standard deviation, standard error, median, minimum, and maximum) will be provided for actual values and changes from baseline to each time point. For categorical variables, patient counts and percentages will be provided.

If any patient dies during the study, a listing of deaths will be provided and all relevant information will be discussed in the patient narrative included in the CSR.

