If data are processed from other sources (eg, central laboratory, bioanalytical laboratory, central image center, electronic diary data, electronic patient-reported outcome [ePRO] tablet), these data will be sent to the investigational center, where they will be retained but not transcribed to the CRF, unless otherwise noted in the protocol. These data may also be sent electronically to the sponsor (or organization performing data management). All patient data must have supportive original source documentation in the medical records, or equivalent, before they are transcribed to the CRF. Data may not be recorded directly on the CRF and considered as source data unless the sponsor provides written instructions specifying which data are permitted to be recorded directly to the CRF.

For patients who enter a study but do not meet entry criteria, at a minimum, data for screening failure reason, demography, and adverse events from the time of informed consent will be entered in the CRF.

Data Quality Control

Data Management is responsible for the accuracy, quality, completeness, and internal consistency of the data from this study. Oversight will be carried out as described in the sponsor's SOPs for clinical studies. Day to day data management tasks for this study are delegated to a contract organization, and these functions may be carried out as described in the SOPs for clinical studies at that organization. These SOPs will be reviewed by the sponsor before the start of data management activities.

Data will be verified by the study monitor using the data source, and reviewed by data management using both automated logical checks and manual review. Data identified as erroneous, or data that are missing, will be referred to the investigational center for resolution through data queries. Any necessary changes will be made in the clinical database, and data review and validation procedures will be repeated as needed. Data from external sources will be compared with the information available in the CDMS and any discrepancies will be queried.

Applicable terms will be coded according to the coding conventions for this study.

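### SAP 8.3 counts adverse events with a missing seriousness flag as non-serious, so any error this causes in an arm's serious-event count is downward

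*SAP*

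**What the plan says.** SAP Section 8.3 (Adverse Events) gives an explicit rule for events with no seriousness flag: "Adverse events with the missing flag indicating serious will be excluded from the summary of serious adverse events". The sentence goes on to place them on the other side, with the non-serious events.

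The same paragraph gives a rule for missing causality. The related-event summary covers "adverse events determined by the investigator to be related to test IMP (defined as related or with missing relationship"), so a missing relationship goes to the worse category. Protocol Section 9.7 has the same causality rule, "adverse events determined by the investigator to be related to test IMP (ie, reasonable possibility) (defined as related or with missing relationship"), and says nothing about missing seriousness. The seriousness rule therefore first appears in the SAP, which prevails where the two documents differ (SAP Introduction). No other section reverses or qualifies it.

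Three provisions limit how often the rule can apply. Protocol 7.1.2 requires the field: "The relationship of each adverse event to IMP and the severity and seriousness of each adverse event, as judged by the investigator, must be recorded". Protocol Appendix L sends gaps back to the site: "Data identified as erroneous, or data that are missing, will be referred to the investigational center for resolution through data queries". And SAP 8.3 keeps unflagged events visible: "Listings will include all adverse events recorded".

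**The concern.** Two missing-data rules in one paragraph point in opposite directions, and no reason is given. For causality the blank goes to the worse category. For seriousness, the field that decides whether an event enters the table a safety reader looks at first, it goes to the better one.

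The non-serious default also contradicts the protocol for one type of event. Protocol 7.1.1 and 7.1.5.1 treat asthma exacerbations as an efficacy variable, kept on their own form and entered as adverse events only when they meet the seriousness criteria. An exacerbation properly recorded as an adverse event is there because it is serious. If its flag is blank, SAP 8.3 calls it non-serious, against the best information available.

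What is at stake is the accuracy of the serious-event summary in the study report. Adverse-event frequency is a secondary safety endpoint (Protocol 2.1).

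**Working it through.** The plan states no figure to reproduce. The check is a comparison of the texts and a counting bound.

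**Inputs**
- Rules for missing seriousness and missing causality: SAP 8.3.
- About 300 randomized patients: Protocol 3.2. Allocation 1:1:1: SAP 2.2. Patients per arm: 300 / 3 = 100.
- Possible reduced sizes of 80 or 90 per arm: SAP 13.1.3.
- Number of missing flags: not given in the documents, so assumed below.

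**Direction within an arm.** Let S be the number of patients with at least one event flagged serious. Let m be the number whose only possibly serious event has no flag. Completed flags are taken as correct.
- Table under SAP 8.3: S.
- True count: between S and S + m.
- Error (table minus truth): between −m and 0, never positive.
- Table if blanks are counted as serious: S + m, with error between 0 and +m.

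Showing both S and S + m brackets the truth; the present rule shows only the lower bound.

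**Size within an arm.** One affected patient changes the arm's percentage by at most 1 / 100 = 1.0 point. At 90 per arm this is 1 / 90 = 1.1 points, and at 80 per arm 1 / 80 = 1.25 points.

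| Assumed m per arm | Largest understatement at 100 per arm |
|---|---|
| 0 | 0 points |
| 1 | 1.0 point |
| 2 | 2.0 points |
| 5 | 5.0 points |

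**Difference between arms.** Let e_A and e_P be the undercounts in an active arm and in placebo, with 0 ≤ e_A ≤ m_A and 0 ≤ e_P ≤ m_P. With equal arm sizes, the error in the count difference (active minus placebo) is e_P − e_A, which lies between −m_A and +m_P. Its sign is not determined by the rule.

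**Where the events go.** SAP 8.3 sends unflagged events to a non-serious summary, but its list of planned summaries names no such table. It covers all, related, serious, withdrawal-causing and special-interest events, with suspected anaphylaxis separately. An unflagged event would appear in the all-event summary, in any other summary whose criteria it meets, and in the listings. No planned table would identify it as unclassified.

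**The case against.** The strongest case against is that the rule will rarely apply. Seriousness is mandatory, missing data are queried, and database lock is meant to confirm that the data are complete and accurate (Protocol Appendix L). A serious event also has its own form, due within 24 hours (Protocol 7.1.2 and 7.1.5.3.1). To be undercounted, it would have to lack its flag and also be missed by, or not reconciled with, that form. This stands, and it is why the expected effect is small.

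The two defaults could also be defended as different in kind. Causality is a judgement, whereas seriousness follows listed outcomes, so the absence of both a flag and a form is some evidence of a non-serious event. In the single-dose part of the Phase 1 study, 19 subjects (16 on active, 3 on placebo) had treatment-emergent events and no serious event was reported, although these were healthy volunteers. This has some force for adverse events in general. It fails for asthma exacerbations, where entry as an adverse event already implies seriousness. Nor does SAP 8.3 require a check that no form exists before the event is called non-serious.

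Finally, counting every blank as serious replaces one one-sided error with another and could create mismatches with the pharmacovigilance record. That is fair. It is met by applying the rule only after query and reconciliation, and by showing the number so that the table can be read both ways.

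A reader might also infer that the rule weakens the interim safety review, made worse by the lack of an independent data monitoring committee. The documents do not support this. The final analyses in the SAP follow the final database lock (SAP 2.5.2). The blinded interim safety review is left to a charter that is not in the documents (SAP 13.2, Protocol 9.13.1), so whether the rule applies there is unknown. Ongoing surveillance does not depend on this table, since serious events are reviewed as sites report them (Protocol 3.4).

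**Conclusion.** The point holds as a low-impact, easily corrected weakness. The rule is explicit, runs opposite to the causality rule beside it, and conflicts with the protocol's recording rule for exacerbations. Any error that it causes in an arm's serious-event count is downward: at most about 1 percentage point per affected patient at about 100 per arm.

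This rests on completed flags being correct and on a number of unresolved flags that the documents do not give. It does not show that the serious-event table will be understated: the table is exact if no flag is missing, or if every unflagged event is truly non-serious. Nor does it show a bias towards the active arms, since the between-arm difference could move either way.

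**What to change.** Replace the sentence in SAP 8.3 with a rule to this effect:

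> An adverse event whose seriousness is still missing after query and reconciliation with the serious adverse event form is counted as serious in the serious-event summary and flagged in the listing. The number of such events and patients is shown by treatment group on a separate line.

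The serious-event table can then be read with and without the unresolved events. In the same edit, either add the non-serious summary to the list of planned tables or remove the reference to it.

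Querying missing data is already procedure under Protocol Appendix L. The new parts are the stated reconciliation step, the reversed default and the reported number. The cost is one SAP sentence, a listing flag and a table line. The downside is that the serious-event count may be slightly high and may include events with no serious adverse event form behind them; the separate line makes that visible.

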8.4. Injection Site Assessments

Local tolerability at the injection site (erythema, ecchymosis, induration, tenderness, warmth, swelling, and pain) will be assessed using standardized scales. Patient reported pain at the injection site will be reported using a standardized 11-point pain intensity numerical response scale (NRS-11) where 0 is “No pain” and 10 is “Worst possible pain”; patients will be asked to

respond to the following question: "How much pain do you feel at the drug injection site, where 0 is 'No pain' and 10 is 'Worst possible pain'?".

Table 2: Severity Assessment of Local Tolerability

Test	Response
Erythema	
 - Absent - Erythema surface diameter 5 to \leq50 mm (mild) - Erythema surface diameter >50 to \leq100 mm (moderate) - Erythema surface diameter >100 mm (severe)
Ecchymosis	
 - Absent - Ecchymosis surface diameter 5 to \leq50 mm (mild) - Ecchymosis surface diameter >50 to \leq100 mm (moderate) - Ecchymosis surface diameter >100 mm (severe)
Induration	
 - Absent - Induration surface diameter 5 to \leq50 mm (mild) - Induration surface diameter >50 to \leq100 mm (moderate) - Indurations surface diameter >100 mm (severe)
Tenderness	
 - None
Warmth	
 - Mild
Swelling	
 - Moderate - Severe

The injection site assessments (erythema, ecchymosis, induration, tenderness, warmth, and swelling) at each visit will be summarized using descriptive statistics. For NRS-11 scale, the worst pain score overall and the pain score at each visit will be summarized descriptively.

In order to account for both placebo and TEV-53275 injections in the 600 mg dose, the summaries will be split into three columns: placebo injections, TEV-53275 injections and total.

The data will be listed using safety analysis set, sorted by treatment group, subject ID, visit, and injection. The study medication administered for each injection will also be listed.

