^{dd} Patients should be trained on the proper use of the handheld device to measure lung function including performing readings prior to taking daily asthma maintenance medication and prior to taking rescue medication within 6 hours of testing (as possible). The patient should be retrained at each visit as indicated.

^{ee} Review compliance with handheld device measurements and with diary entries, including the proper use in relation to asthma maintenance medication and rescue medication use/timing.

^{ff} Patients who meet the requirements for randomization, after the procedures for specimen collection and other testing, will each receive 4 sc injections in the abdomen, administered by a qualified health care provider (according to local regulations) who is prepared to manage anaphylaxis, as described in the study reference manual. The kit number and location will be recorded in the source documents and entered in the CRF for each of the 4 injection site locations along with any injection site reactions evaluated at approximately 1 hour after dosing. If the patient develops clinical symptoms, vital signs should be recorded and the patient should be assessed for anaphylaxis/hypersensitivity reactions. Before leaving the clinic, patients will additionally be advised of symptoms/signs for which they should seek medical advice or medical treatment.

^{gg} Evaluation of injection site for reaction will be performed at approximately 1 hour after dosing using the injection site CRF. Injection site findings will not be captured as adverse events unless they fulfill characteristics that are beyond those in the specified forms/scales (eg, necrosis, abscess, etc.) or fulfill seriousness criteria; if fulfilled, they must be recorded and reported.

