7.8. Assessment of Local Tolerability and Pain

Local tolerability at the injection site (erythema, ecchymosis, induration, tenderness, warmth, swelling, and pain) will be assessed using standardized scales. Patient reported pain at the injection site will be reported using a standardized 11-point pain intensity numerical response scale (NRS-11) where 0 is “No pain” and 10 is “Worst possible pain”; patients will be asked to respond to the following question: “How much pain do you feel at the drug injection site, where 0 is ‘No pain’ and 10 is ‘Worst possible pain’?”.

The assessments will be performed at approximately 1 hour after dosing ([Table 2](#)).

Severity of local tolerability symptoms should be assessed as described in [Table 6](#). Erythema, ecchymosis, and induration will be considered only if they reach a diameter of at least 5 mm. The surface diameter in millimeters will be recorded and erythema, induration, and ecchymosis at the injection site will be graded according to the diameter measurements: Absent, 5 to \leq 50 mm (mild), $>$ 50 to \leq 100 mm (moderate), and $>$ 100 mm (severe). Induration must be assessed by careful superficial palpation avoiding pressuring or squeezing the injection site.

In cases where symptoms do not resolve, assessments will proceed at each ambulatory visit. Appropriate treatment may be provided if necessary, in which case it must be recorded as concomitant medication. In case the site(s) of injection need visual representation, in addition to comments in the source documents, the injection site(s) may be photographed along with a metric ruler and patient identification number for later review. Any features that could be used to identify the patient will not be captured on the photograph.

Table 6: Severity Assessment of Local Tolerability

Test	Response
Erythema	
- Absent- Erythema surface diameter 5 to \leq50 mm (mild)- Erythema surface diameter >50 to \leq100 mm (moderate)- Erythema surface diameter >100 mm (severe)
Ecchymosis	
- Absent- Ecchymosis surface diameter 5 to \leq50 mm (mild)- Ecchymosis surface diameter >50 to \leq100 mm (moderate)- Ecchymosis surface diameter >100 mm (severe)
Induration	
- Absent- Induration surface diameter 5 to \leq50 mm (mild)- Induration surface diameter >50 to \leq100 mm (moderate)- Indurations surface diameter >100 mm (severe)

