At this visit the patient's diary data should be reviewed prior to formal lung function testing, laboratory testing and the various questionnaires to ensure compliance with diary entries and to determine if lung function, symptoms and rescue medication use meet the randomization criteria. If the patient fails to meet the diary requirements, the patient will be considered a randomization failure. Further procedures for V3 will only be conducted for patients who meet the diary requirements.

The following procedures will be performed:

- review inclusion and exclusion criteria
- review randomization criteria
- review compliance with diary and study randomization requirements
- full physical examination (to include, at a minimum, head, eyes, ears, nose, and throat [HEENT], chest, cardiovascular, abdominal, skin, and neurological examination)
- pulmonary function testing (spirometry)
- hematology (CBC with differential analysis)
- fasting serum chemistry tests
- obtain a blood sample for Phadiatop Allergy Test and Total IgE
- obtain a blood sample for pharmacogenetics (confirm patient has provided informed consent for this procedure)
- obtain a blood sample for pharmacokinetics (serum IMP concentration)
- obtain a blood sample for serum anti-drug antibody (ADA) assay
- obtain a blood sample for biomarker interleukin 5 (IL-5) analysis
- urinalysis
- urine pregnancy test for women of childbearing potential (β HCG)
- 12-lead electrocardiogram (ECG) in triplicate. Each ECG will be taken within 1 to 5 minutes of the previous one.
- vital signs measurements
- [REDACTED]
- [REDACTED]
- complete ACQ-6
- Asthma Control Test (ACT)

- Standardized Asthma Quality of Life Questionnaire (AQLQ[S])
- [REDACTED]
- conduct training on handheld device and review diary use and compliance
- perform randomization and treatment assignment in interactive response technology (IRT) after confirming eligibility including diary and pulmonary function testing, ACQ 6 score and the remaining randomization criteria have been met.
- investigational medicinal product (IMP) dosing (Note: dosing may not occur until all clinical laboratory samples, and questionnaires have been completed). Doses will be administered by a qualified health care provider (according to local regulations) who is prepared to manage anaphylaxis
- postdose observation period of 1 hour
- injection site evaluation
- dispense rescue medication (if needed)
- collect rescue medication
- assess CAEs

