4. GENERAL ISSUES FOR DATA ANALYSIS

4.1. General

Descriptive statistics for continuous variables include count (n), mean, SD, standard error (SE), median, minimum, and maximum. In addition, for TEV-53275 concentration, percentage coefficient of variation (%CV) and geometric mean will also be calculated. Descriptive statistics for categorical variables include patient counts and percentages, and a missing category will be displayed as appropriate.

Summaries of potentially clinically significant abnormal values for clinical laboratory tests and vital signs values will include all postbaseline values (including scheduled, unscheduled, and early withdrawal visits).

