4.3. Handling Withdrawals and Missing Data

For all variables, only the observed data from the patients will be used in the statistical analyses, ie, there is no plan to estimate missing data, unless otherwise specified.

Dates that have incomplete information (the month and year or just the year is available) will be estimated for the purpose of calculating variables that are dependent on time if necessary. Day will be estimated as the first day (01) of the month (if month and year of partial date are available) or middle (July 1) of the year (if only year is available), unless otherwise noted. The imputations for partial dates are only for calculation purpose. Original date variables will not be modified. Listings will list dates as collected.

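### SAP 8.4 summarises injection-site findings and pain by visit, but after the 1-hour check only patients with unresolved symptoms are due for scoring, so later-visit mean pain does not validly compare the arms

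*SAP*

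**What the plan says.** **When sites are scored.** Protocol 7.8: "The assessments will be performed at approximately 1 hour after dosing". The Table 2 footnote in Protocol 3.5 agrees: "Evaluation of injection site for reaction will be performed at approximately 1 hour after dosing using the injection site CRF". Appendix B lists "injection site evaluation" at V3, the dosing visit. It does not appear in the lists for V4 to V10, unscheduled visits or the early withdrawal visit.

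**Who is scored later.** Protocol 7.8: "In cases where symptoms do not resolve, assessments will proceed at each ambulatory visit". No later scoring is scheduled for patients who never reacted or whose reaction has cleared.

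**What is summarised.** SAP 8.4 states that the six graded findings (erythema, ecchymosis, induration, tenderness, warmth, swelling) "at each visit will be summarized using descriptive statistics", and that for pain "the worst pain score overall and the pain score at each visit will be summarized descriptively". SAP 4.1 defines the content: "Descriptive statistics for continuous variables include count (n), mean, SD, standard error (SE), median, minimum, and maximum". A mean pain score by visit is therefore planned. SAP 8.4 also splits the summaries by type of injection (placebo, TEV-53275, total), because the 600 mg dose mixes the two.

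**How unassessed patients are treated.** SAP 4.3: "only the observed data from the patients will be used in the statistical analyses", with no estimation of missing values unless otherwise specified. SAP 8.4 specifies no exception and gives no denominator for visits after V3.

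**The concern.** At V3 every dosed patient is due for a score, so the summary describes the whole arm. From V4 on, whether a patient is due for a score depends on the outcome being measured. Patients with no reaction, or with one that has cleared, leave the statistic. What remains says how bad the followed-up cases are, not how common persistence is. An arm with many persisting mild reactions can then look better than an arm with a few worse ones.

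Local tolerability is a secondary safety endpoint under an objective that compares with placebo. Protocol 7.1.7 and 7.8 keep injection-site findings out of adverse event reporting unless they go beyond the scales or are serious. For ordinary reactions, the SAP 8.4 tables are thus the main planned summary, and the adverse event tables will not correct a misleading one.

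**Working it through.** **No figure to reproduce.** The documents state no rate, mean or sample size for injection-site findings. The check is a comparison of the texts, then arithmetic on assumed inputs.

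**Texts side by side**

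1. Scheduled scoring: once, at V3 (Protocol 7.8, the Table 2 footnote, Appendix B). The part of the Table 2 grid that would hold this row is not readable in the public copy, so this rests on the footnote and Appendix B.
2. Later scoring: conditional on unresolved symptoms (Protocol 7.8).
3. Statistic: by visit, including the mean (SAP 8.4 with 4.1).
4. Data used: observed only, no exception (SAP 4.3, 8.4).

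Together, the later-visit mean is taken over patients selected for having had symptoms that did not resolve.

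**Inputs for the illustration**

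- N = 100 per arm: 300 randomised in a 1:1:1 ratio (protocol synopsis), all assumed dosed and attending.
- k = patients reassessed at a later visit, m = their mean pain; A = active, B = placebo. Not in the documents; assumed ranges: kA 3 to 20, kB 1 to 5, mA 1.5 to 3, mB 2 to 4.

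**Formulas**

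- Mean as planned (observed only) = m.
- Share of the arm still followed = k/N.
- Burden over the whole arm = k × m / N. This counts patients not reassessed as 0. It is a yardstick for this check only, not a proposed table entry.
- With equal N, the order reverses when mA < mB but kA × mA > kB × mB, that is when 1 < mB/mA < kA/kB.

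| kA, mA | kB, mB | Planned means, A vs B | k/N, A vs B | k × m / N, A vs B | Order reversed? |
|---|---|---|---|---|---|
| 20, 2 | 5, 3 | 2.0 vs 3.0 | 20% vs 5% | 0.40 vs 0.15 | yes |
| 10, 2 | 5, 3 | 2.0 vs 3.0 | 10% vs 5% | 0.20 vs 0.15 | yes |
| 8, 2 | 5, 3 | 2.0 vs 3.0 | 8% vs 5% | 0.16 vs 0.15 | yes |
| 7, 2 | 5, 3 | 2.0 vs 3.0 | 7% vs 5% | 0.14 vs 0.15 | no |
| 5, 2 | 5, 3 | 2.0 vs 3.0 | 5% vs 5% | 0.10 vs 0.15 | no |
| 10, 1.5 | 2, 3 | 1.5 vs 3.0 | 10% vs 2% | 0.15 vs 0.06 | yes |
| 3, 2 | 1, 4 | 2.0 vs 4.0 | 3% vs 1% | 0.06 vs 0.04 | yes |
| 20, 3 | 5, 2 | 3.0 vs 2.0 | 20% vs 5% | 0.60 vs 0.10 | no |

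For rows 1 to 5, mB/mA = 3/2 = 1.5, so reversal needs kA/kB above 1.5: 8/5 = 1.6 reverses, 7/5 = 1.4 does not. In the last row the arm with more reassessed patients also has the higher mean, and nothing reverses.

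**Graded findings.** Suppose 4 of 20 reassessed active patients and 2 of 5 reassessed placebo patients have a moderate or worse finding. Of those assessed: 4/20 = 20% vs 2/5 = 40%. Of all dosed: 4/100 = 4% vs 2/100 = 2%. The raw counts, 4 vs 2, do not reverse. The risk lies in the mean and in a percentage whose denominator is the patients assessed.

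**The case against.** Several counter-arguments have force.

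- **The denominator is unstated, not wrong.** SAP 8.1 uses the safety set, and SAP 4.1 allows a missing category where appropriate. A programmer could compute percentages over the safety set. This stands for percentages, but it does not help the mean, which under SAP 4.3 can only use observed scores.
- **The selection would show.** SAP 4.1 requires n beside the mean, and SAP 8.4 lists the data by patient, visit and injection. In the first row of the table a reader would see n = 20 and n = 5. This stands in part: n reveals the selection but does not make the means comparable.
- **The main results are sound.** All dosed patients are due for the 1-hour score, and worst pain overall draws on it. This stands.
- **Later numbers will be small.** Protocol 1.3.1 reports that single-dose Phase 1 findings were all mild except in one subject, whose moderate findings resolved over 4 hours. V4 is on day 3±2. This stands and limits the impact, although a mean over a handful of selected patients is also harder to interpret.
- **Scoring the unassessed as absent with pain 0 creates data nobody collected.** A late-onset reaction that was never scored would be recorded as absent. This stands, and the fix below does not impute.

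A reader might also infer that later-visit percentages must be close to 100%, or that every later-visit figure describes persistent cases only. The documents do not support either. There are six graded findings plus pain, and four injections per patient. Someone followed for erythema can score none on tenderness and 0 on pain, and someone called back can be found to have cleared.

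**Conclusion.** The point holds in a limited form. After V3, the mean pain score and any percentage of those assessed rest on patients selected by outcome, so they are not a valid comparison between arms. This follows from Protocol 7.8 read with SAP 8.4, 4.1 and 4.3 and needs no assumption about rates. The same selection reaches the columns by injection type.

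The size cannot be derived from the documents. Reversal of the arms is a possibility shown with assumed counts. It needs the ratio of mean pain (placebo to active) to lie between 1 and the ratio of reassessed patients (active to placebo). It would go too far to say that reversal is expected, or that the trial's local tolerability assessment as a whole is unreliable: the 1-hour summary is unaffected, worst pain overall is largely unaffected, and the data are descriptive with no test or decision rule attached. The practical impact is modest, and the text is cheap to correct.

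**What to change.** Amend SAP 8.4 as follows.

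1. Make the 1-hour assessment at V3 the by-arm summary of severity and pain. Keep worst pain overall.
2. For visits after V3, report the number and percentage of patients with a persisting finding, with all safety-set patients in the arm attending that visit as denominator.
3. For the injection-type columns, use all injections of that type given to those patients. At 300 mg per injection (3 mL at 100 mg/mL), the 600 mg dose is 600/300 = 2 TEV-53275 and 4 − 2 = 2 placebo injections, so 100 attending patients give 200 of each.
4. Show severity and pain among reassessed patients only as a separate row, labelled as follow-up of unresolved cases. Do not present later-visit mean pain as an arm comparison.
5. Do not enter absent or pain 0 as if observed. State that patients not reassessed are taken to have no known unresolved finding.

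The cost is one paragraph of SAP text and a small amount of programming, with no new data. The downside is that a late-onset reaction that was never scored is not counted. That gap exists under the current plan too, and a footnote to the table should say so.
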